Dual antiplatelet therapy with aspirin and a P2Y₁₂ adenosine diphosphate (ADP) receptor inhibitor is standard therapy for prevention of thrombotic complications of percutaneous coronary intervention (PCI). The American College of Cardiology (ACC), American Heart Association (AHA), and European Society of Cardiology (ESC) practice guidelines recommend dual antiplatelet therapy with aspirin and an ADP receptor inhibitor in patients with acute coronary syndromes (ACS), particularly among those undergoing PCI (Jneid et al. 2012; Hamm et al. 2012). Landmark studies such as CURE and CLARITY-TIMI 28 established the benefit of long-term clopidogrel for up to 1 year in subjects with ACS who undergo PCI (Mehta et al. 2001; Sabatine et al. 2005). Significant variability in the response to clopidogrel has been observed secondary to genetic polymorphisms and pharmacodynamic interactions, with some individuals having minimal inhibition of ADP-induced platelet aggregation leading to the concern that some patients may be at increased risk for thrombotic events (Mega et al. 2011; Mega et al. 2010; Mega et al. 2009).

Results from TRITON-TIMI 38 established the superior efficacy of prasugrel in combination with aspirin over clopidogrel plus aspirin in reducing ischemic events in ACS patients managed with PCI (Wiviott et al. 2007). Compared with clopidogrel, prasugrel caused higher rates of major bleeding, particularly in patients with advanced age, low body weight, previous stroke or transient ischemic attack. Since its United States (US) approval in 2009, there are few observational studies that directly compare outcomes between prasugrel and clopidogrel for ischemic and bleeding events. The TRANSLATE-ACS registry was a prospective observational study of approximately 12,000 patients with myocardial infarction ([MI], ST-segment elevation myocardial infarction [STEMI] or non-ST-segment elevation myocardial infarction [NSTEMI]) managed with PCI (Chin et al. 2011). The study evaluated the comparative effectiveness and safety of prasugrel compared with clopidogrel in the usual care environment (Wang et al. 2014). However, as long-term follow-up was prospectively collected, patient informed consent was required that limited the ability to collect data on all MI patients managed with a PCI. Therefore, there are a large number of eligible patients who were not included in the TRANSLATE-ACS database because they either did not give consent or were discharged prior to being identified and consent obtained.

A prior comparative retrospective, observational analysis between clopidogrel and prasugrel using the Premier claims database assessed the impact of treatment group on readmission rates for MI or bleeding (Bae et al. 2014). Adjusted results showed that prasugrel was associated with significantly lower acute myocardial infarction (AMI)-related rehospitalizations compared with clopidogrel 30 and 90 days post-discharge. Additionally, adjusted results showed no significant difference in bleeding-related rehospitalization rates between prasugrel- and clopidogrel-treated patients (Bae et al. 2014). However, analyses conducted in payer databases provide less clinical detail than registries (for example, the ACC National Cardiovascular Data Registry [NCDR] CathPCI Registry®) or prospective observational studies. For instance, pre-existing conditions (prior to the index admission) may be missed. Consequently, the true baseline profile of the cohorts may be inadequately determined (for example, missing a prior MI or stroke that may have occurred more than 12 months before the index hospitalization) resulting in inadequate adjustment of the data for unmeasured differences in known confounders. Additionally, payer databases are dependent upon claims made on discharge from the hospital, and may not differentiate from the primary event or the secondary event, especially if secondary diagnoses are allowed in the definition of an outcome event.

Hence, an observational retrospective database analysis using data collected from patients and/or their medical records at the time of index hospitalization with post-hospitalization follow-up will provide important information and will allow better adjustment for baseline differences and a more accurate representation of the clinical results. Study B020 will utilize pooled databases from academic institutions, where clinical data is routinely collected on all patients undergoing PCI both during and after the index hospitalization, to compare clinical and economic outcomes between clopidogrel and prasugrel. This approach will provide a more appropriately designed baseline characteristic collection to adjust for known patient characteristic differences between prasugrel and clopidogrel treatment groups in ACS patients treated with PCI. Additionally, this study will include many of the patients who were not able to be enrolled in TRANSLATE-ACS, such as those with unstable angina, as their data is already captured in these institutional databases. The databases from these institutions collect a large amount of data as either part of or consistent with the ACC NCDR CathPCI Registry, which includes not only clinical characteristics but also detailed procedural characteristics of patients. Additionally, as these data are

entered from patient records based on the clinical evaluation, there is no pre-specified time window for capturing prior events. The centers participating in this study have also followed these patients post-hospitalization as part of the on-going evaluation of their results.

4 Study Objectives and Endpoints

To describe and compare the clinical and angiographic profiles of ACS patients managed with percutaneous coronary intervention with stent implantation and treated with prasugrel or clopidogrel.

4.1 Primary Objectives

To compare major adverse cardiac event (MACE) outcomes (the composite occurrence of all-cause death, MI, stroke, or unplanned coronary revascularization) within 90 days of index PCI in patients with ACS treated with prasugrel or clopidogrel.

4.2 Secondary Objectives

1. To examine the following clinical outcomes for ACS patients managed with PCI initiating treatment with prasugrel versus those initiating treatment with clopidogrel:
 - a. To describe differences in the demographic, clinical, and angiographic profiles. To compare the composite MACE endpoint within 30, 180, and 365 days following index PCI.
 - b. To compare the individual components of the MACE endpoint (all-cause death, MI, stroke, and unplanned revascularization) within 30, 90, 180, and 365 days following index PCI.
2. To compare all in and out of hospital bleeding events within 30, 90, 180 and 365 days from index PCI. To compare bleeding-related rehospitalizations within 30, 90, 180, and 365 days from index hospital discharge with prasugrel versus clopidogrel
3. To compare post-procedural (in-hospital) MACE and bleeding events.
4. To compare Academic Research Consortium (ARC) defined definite/probable stent thrombosis at 30, 90, 180, and 365 days following index PCI with prasugrel versus clopidogrel.
5. To compare MACE and bleeding events at 30, 90, 180 and 365 days following index PCI in the following pre-specified subgroups:
 1. ACS-PCI patients with no prior transient ischemic attack (TIA) or stroke
 2. ACS-PCI patients with no prior TIA or stroke and are:
 - a. <75 years of age, or

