3.2.2. Secondary Objectives

1. To examine the following clinical outcomes for ACS patients managed with PCI initiating treatment with prasugrel versus those treated with clopidogrel:

- a. To describe differences in the clinical and angiographic profiles of ACS patients managed with PCI treated with prasugrel versus clopidogrel
 - b. To compare the composite MACE endpoint at 30, 180, and 365 days following index hospital admission
 - c. To compare the individual components of the MACE endpoint (all-cause death, MI, stroke, and unplanned revascularization) at 30, 90, 180, and 365 days following index hospital admission
 - d. To compare prasugrel with clopidogrel with regard to the following non-fatal individual components of MACE at 90, 180, and 365 days following index hospital admission:
 1. new MI
 2. unplanned revascularization
 3. stroke
 - e. To compare all bleeding events or transfusions during index hospital
 - f. To compare bleeding-related rehospitalizations within 30, 90, 180, and 365 days from index hospital discharge with prasugrel compared with clopidogrel
 - g. To compare Academic Research Consortium (ARC) defined definite/probable stent thrombosis at 30, 90, and 365 days following index hospital admission with prasugrel versus clopidogrel
 - h. To compare composite MACE and bleeding events at 30, 90, 180, and 365 days following index hospital admission in the following pre-specified subgroups:
 1. ACS-PCI patients with no prior transient ischemic attack (TIA) or stroke
 2. ACS-PCI patients with no prior history of TIA or stroke and are:
 - a. <75 years of age, or
 - b. If ≥ 75 years of age, have diabetes mellitus or a history of MI
 3. Age ≥ 75 years
 4. Diabetes mellitus

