12/31/2012		
Unplanned revascularization	0=no, 1=yes	Hospitalization for unplanned revascularization with CABG or PCI after index PCI
Unplanned revascularization date	DDMMYYYY	date of event
Number of unplanned revascularization hospitalization until 12/31/2012		Total number of unplanned revascularization hospitalization from 1/1/2010 - 12/31/2012
Bleeding	0=no, 1=yes	Hospitalization for bleeding after index PCI
Bleeding date	DDMMYYYY	date of event
Number of bleeding hospitalization until 12/31/2012		Total number of bleeding hospitalizations from 1/1/2010 - 12/31/2012
Type of Bleeding	1=access site; 2=GI; 3=GU; 4=CNS; 5=other; 6=unknown	1)access site 2) GI 3) GU 4) CNS 5) Other 6) Unknown
Stroke	0=no, 1=yes	Was the patient diagnosed as having a stroke
Stroke date	DDMMYYYY	Date of event
Stroke type	1=ischemic; 2=hemorrhagic; 3= unknown	1) Ischemic 2) hemorrhagic
Number of stroke hospitalizations until 12/31/2012		Total number of stroke hospitalizations from 1/1/2010 - 12/31/2012
Definite/Prob ST	0=no, 1=yes	Hospitalizations for Definite/Probable Stent Thrombosis
Definite/Prob ST date	DDMMYYYY	Date of Event

Data Field Term	VALUE	Description/Definition
last follow up date	DDMMYYYY	Last date of encounter with patient

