5.2 Data Source

Each of the academic centers selected to participate in Study B020 will provide information on the patterns of antiplatelet use for ACS patients undergoing PCI and specifically their volumes for the period from 01 January 2010 to 30 June 2013 through a site selection questionnaire. Each of the participating centers maintains high quality institutional databases of both in-hospital and post-discharge follow-up events. The data in these sets are derived primarily from the NCDR CathPCI database while the post-discharge follow-up data is physician-determined diagnoses at time of hospitalization as described in Section 4.3. The index hospital data is collected at most sites according to the definitions used in CathPCI registry data collection form. No adjudication of the data will be performed. These databases do not typically include prescriptions, adherence, or outpatient encounters. This project will extract data from the participating centers using extraction sheets with standardized definitions. Extracted data will be entered in a Core Study Dataset for data analyses.

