Post Procedure Vascular Complication	0=no, 1=yes	
Indicate if the patient experienced any other vascular complications (excluding external bleeding or hematomas) at the percutaneous entry site that required treatment or intervention. Note: Code 'yes' for patients treated with IV therapy for loss of distal pulse. For patients with extended hospital stays, restrict coding of post-procedure events to 30 days after the last procedure. Target Value: Any occurrence between start of procedure and until next procedure or discharge. Vascular complications can include, but are not limited to, access site occlusions, peripheral embolizations, dissections, pseudoaneurysms and/or AV fistulas. Any noted vascular complication must have had an intervention such as a fibrin injection, angioplasty, or surgical repair to qualify. Prolonged pressure does not qualify as an intervention, but ultrasonic guided compression after making a diagnosis of pseudoaneurysm does qualify. A retroperitoneal bleed or hematoma requiring transfusion is not a

		vascular complication under this data element. To qualify, this adverse outcome should be attributable to this procedure and not related to a previous or subsequent procedure.
Post Procedure Blood Transfusion	0=no, 1=yes	Indicate if there was a transfusion(s) of either whole blood or packed red blood cells. For patients with extended hospital stays, restrict coding of post-procedure events to 30 days after the last procedure. Target Value: Any occurrence between start of procedure and until next procedure or discharge.
Units of Blood Transfused	##	Number of prbc transfused. Leave as missing if pp_trans = 0.
Post Procedure Bleeding event (72 hours)	0=no, 1=yes	Note(s): A patient who was actively bleeding with coffee ground emesis pre-procedure should not qualify as bleeding. However, a patient with peptic ulcer disease with no noted or active bleeding prior to procedure who starts bleeding after the procedure would qualify as a 'yes'.
Death (all)	0=no, 1=yes	Report of patient death occurring within one year of procedure date
Death (all) date	DDMMYYYY	Date of death
Type of Death	1=cardiac; 2=noncardiac; 3=unknown	Enter type of death
Myocardial infarction within one year of procedure	0=no, 1=yes	Hospitalization for acute (spontaneous) MI within one year of index procedure date
Myocardial infarction date	DDMMYYYY	Date of event

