Number of acute MI hospitalization within one year of procedure	##	Total number of acute MI hospitalization within one year of index procedure date

Unplanned revascularization within one year of procedure	0=no, 1=yes	Hospitalization for unplanned revascularization with CABG or PCI within one year of index procedure date
Unplanned revascularization date	DDMMYYYY	Date of event
Number of unplanned revascularization hospitalization within one year of procedure	##	Total number of unplanned revascularization hospitalization within one year of index procedure date
Bleeding within one year of procedure	0=no, 1=yes	Hospitalization for bleeding within one year of index procedure date
Bleeding date	DDMMYYYY	Date of event
Number of bleeding hospitalization within one year of procedure	##	Total number of bleeding hospitalizations within one year of index procedure date.
Type of Bleeding	1=access site; 2=GI; 3=GU; 4=CNS; 5=other; 6=unknown	1)Access site 2) GI 3) GU 4) CNS 5) Other 6)Unknown
Stroke within one year of procedure	0=no, 1=yes	Was the patient diagnosed as having a stroke within one year of index procedure date
Stroke date	DDMMYYYY	Date of event
Stroke type	1=ischemic; 2=hemorrhagic; 3=unknown	1) Ischemic 2) Hemorrhagic
Number of stroke hospitalizations within one year of procedure	##	Total number of stroke hospitalizations within one year of index procedure date.
Definite/Probable ST	0=no, 1=yes	Hospitalizations for Definite/Probable Stent Thrombosis
Definite/Probable ST date	DDMMYYYY	Date of Event

last follow up date	DDMMYYYY	Last date of encounter with patient
---------------------	----------	-------------------------------------

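### The SAP's all-bleeding outcome is built from a 72-hour index-stay flag and bleeding hospitalizations only, so some bleeds between 72 hours and discharge are not counted, and whether transfusion counts is left undefined

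*SAP*

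**What the plan says.** SAP 4.2 item 2 undertakes "To compare all in and out of hospital bleeding events within 30, 90, 180 and 365 days from index PCI". The same item then lists bleeding-related rehospitalization as a separate comparison, and item 3 adds "To compare post-procedural (in-hospital) MACE and bleeding events". Section 9 plans Kaplan-Meier curves for any bleeding at 90 days and 1 year. Table 4, whose title covers events in and out of hospital, has a bleeding row with Kaplan-Meier rates and hazard ratios.

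The fields in SAP Section 13 (Attachment 1) are narrower. Index-stay bleeding is a yes/no item labelled "Post Procedure Bleeding event (72 hours", with no date. Later bleeding is "Hospitalization for bleeding within one year of index procedure date", with a date. The Protocol's Attachment 1 has the same 72-hour item and defines later bleeding as "Hospitalization for bleeding after index PCI".

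Transfusion has its own yes/no field, also undated, whose window is "Any occurrence between start of procedure and until next procedure or discharge". It is reported in Table 3 beside the 72-hour bleeding row.

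Protocol 3.2.2(e) worded the index-stay objective as "To compare all bleeding events or transfusions during index hospital". SAP items 2 and 3 name bleeding without transfusion. SAP 4.3 defines death, stent thrombosis, MI, stroke, unplanned revascularization and MACE, but not bleeding.

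**The concern.** The outcome's name and its data do not match. A patient who bleeds on day 5 of a 9-day stay is outside the 72-hour flag and has not been hospitalized for bleeding, so neither bleeding field records the event.

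Both documents name major bleeding as the harm that was higher with prasugrel in the earlier randomized comparison. A reader of Table 4 or the Section 9 curve would take the row as the study's full account of that harm. The other in-hospital events in Table 3 (MI, shock, heart failure, stroke, tamponade, dialysis, vascular complication, transfusion) run to the next procedure or discharge. Item 3 would therefore compare ischemic events over the stay with bleeding over three days.

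Because bleeding is undefined, whether transfusion counts could also be settled after the results have been seen.

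**Working it through.** The plan states no figure on this point, so there is none to reproduce. The check is which field, if any, records each kind of bleed.

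| Bleed | Field that records it (SAP Attachment 1) | Counted as bleeding? |
|---|---|---|
| Index stay, within 72 hours | 72-hour bleeding flag | Yes |
| Index stay, after 72 hours, transfused before any next procedure | Transfusion field | Not stated |
| Index stay, after 72 hours, hemorrhagic stroke | Post-procedure stroke field, to next procedure or discharge | Not stated; recorded as stroke |
| Index stay, after 72 hours, neither of these | No bleeding field | Lost |
| After discharge, admitted for bleeding | Hospitalization for bleeding | Yes |
| After discharge, not admitted | None | Lost |

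Other fields do not close the gap. Nadir hemoglobin is also limited to 72 hours. The vascular complication field excludes external bleeding and hematomas, and says that a retroperitoneal bleed or hematoma requiring transfusion does not qualify. On the last row, SAP 5.2 says "These databases do not typically include prescriptions, adherence, or outpatient encounters".

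The in-hospital part matters because item 2 already compares bleeding rehospitalization separately. Apart from the time origin (PCI or discharge), what the wider outcome adds is index-stay bleeding, and that is where the gap lies.

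**Length of the uncovered period.** Uncovered days = discharge day after PCI − 3, and zero for discharge by day 3. Share of a window = uncovered days / window length. The documents give no length of stay, so the discharge days below are assumptions.

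| Discharge day (assumed) | Uncovered days | Share of 30 days | Share of 90 days |
|---|---|---|---|
| 3 or earlier | 0 | 0% | 0% |
| 4 | 1 | 3.3% | 1.1% |
| 5 | 2 | 6.7% | 2.2% |
| 7 | 4 | 13.3% | 4.4% |
| 10 | 7 | 23.3% | 7.8% |

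For day 7, for example: 7 − 3 = 4; 4/30 = 13.3%; 4/90 = 4.4%. These are shares of time, not of bleeds, because bleeding risk is not constant over the window.

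**Event time.** Table 4 needs a time from index PCI for every event, but the index-stay bleeding and transfusion fields carry no date and the SAP gives no rule for assigning one.

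**The case against.** The strongest reply is that little is truly missing. Transfusion is still collected past 72 hours, with units, and has its own Table 3 row. In-hospital hemorrhagic stroke is collected to the next procedure or discharge. Patients discharged within 72 hours of PCI have no gap, and for discharge on days 4 to 7 the uncovered time is 1.1% to 4.4% of the 90-day window. The lack of outpatient data is disclosed. Elsewhere (SAP 6.1, fifth sensitivity analysis) out-of-hospital MACE means events after the index stay, so out-of-hospital bleeding may simply mean readmission. Bleeding is a secondary outcome.

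Much of this stands, and it rules out several stronger readings that a reader might infer:

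- *Every bleed from 72 hours to discharge is missed.* Not so. Transfused bleeds and hemorrhagic strokes in that period are recorded, although not as bleeding.
- *The SAP removed transfusion from the bleeding outcome.* It is absent from the objectives but not from the dataset or Table 3. Since the Table 4 row is undefined, its exclusion there is an inference.
- *SAP 7.1 discards events after a repeat PCI.* The first-procedure rule concerns clinical, demographic and procedural details. Events have a separate rule, under which the first of each type is reported. Only the transfusion field's own stop at the next procedure limits capture.
- *A count of lost bleeds can be given.* Assuming 2–5% index-stay bleeding in 8,606 patients, with 10–30% of it after 72 hours, gives about 17 (8,606 × 2% × 10%) to 129 (8,606 × 5% × 30%). Neither percentage is in the documents, and the count would include transfused bleeds that are recorded.

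The reply does not supply a definition of bleeding, a place for late non-transfused bleeds, or a basis for the words all and any.

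**Conclusion.** The point holds as a mismatch between the outcome's label and its data, together with a missing definition. Bleeds after 72 hours and before discharge that are neither transfused nor hemorrhagic strokes are lost. Transfused ones in that period count only if transfusion is part of the outcome, which the Protocol said for the index stay and the SAP does not.

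The gap is confined to patients who stay more than 72 hours after PCI. Its size cannot be computed from the documents. The direction of any effect on the hazard ratio is also unknown. The plan expects the groups to differ at baseline, so length of stay could differ between them, but nothing in the documents shows that it does or which way. What can be said is that index-stay bleeding is under-counted in absolute terms.

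This rests on reading the 72-hour label as the field's window, since the field states no other. The primary 90-day MACE outcome is not affected. The change should be made because it alters both the reported bleeding result and what that result can claim.

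**What to change.** 1. In SAP 4.3, define index-stay bleeding as the 72-hour flag or the existing transfusion field (to next procedure or discharge). This restores the Protocol 3.2.2(e) wording.
2. Use that composite plus hospitalization for bleeding as the outcome in Table 4 and Section 9.
3. State the event time assigned to the undated index-stay fields, before outcomes are analyzed.
4. Relabel the outcome as in-hospital bleeding (72 hours) or transfusion, or hospitalization for bleeding, in place of all or any bleeding.
5. Extend either index-stay window to discharge only where a center's database already holds the data, and record which centers did so, because capture would then differ by center.

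Items 1 to 4 need only SAP text and fields already collected. Item 5 may be impossible at some centers: the data come mainly from CathPCI (SAP 5.2), and Protocol 3.5 rules out chart review and review of free text. Where it is impossible, late non-transfused bleeds remain uncounted, and the new label says so honestly.

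The cost is some loss of specificity, because not every transfusion is given for bleeding. Reporting the components separately deals with this; Table 3 already has both index-stay rows.
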